## 3.2 Analysis Populations

### 3.2.1 *Safety Population (SAF)*

The safety population (SAF) includes all participants who received at least one dose of EDG-5506. All safety analyses will be based on the SAF. The SAF will be used for all participant disposition, demographics, safety measures and functional/clinical assessments.

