5.1. Inclusion Criteria

Participants are eligible to be included in the study only if all the following criteria apply:

1. Type of Participant and Disease Characteristics

Participants who have completed Study EDG-5506-001.

Participants who were not from Study EDG-5506-001 must meet the following:

- a. Male sex at birth and aged 18 to 55 years inclusive at time of consent.
- b. Documented dystrophin mutation with phenotype consistent with BMD.
- c. Ambulatory at Screening (defined as ability to complete 100 meter [m] timed test, with or without assistance).
- d. Body weight \geq 50 kg at the Screening visit.
- e. Body mass index (BMI) between 20 and 34 kg/m² inclusive.

2. Sex and Contraceptive/Barrier Requirements

Female sexual partners of male participants must use highly effective contraception (<1% failure rate per year) through 6 months after last dose.

- f. Participants must agree to not donate sperm during the study and for at least 6 months after last dose.

3. Informed Consent

Capable of giving signed informed consent as described in [Appendix A](#), which includes compliance with the requirements and restrictions listed in the informed consent form (ICF) and in this protocol.

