### 3.1.4 Change-from-Baseline (CFB)

The CFB will be calculated by subtracting the BL values from the individual post-dose values. If the BL value is missing, the missed measurement will be replaced with the last previously-populated value from the patient's visits, including unscheduled visits, in a last-observation-carried-forward (LOCF) approach. Missing post-BL values will not be replaced. That is, the LOCF approach will only be utilized in replacing BL values.

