### 3.1.5 Summary Statistics

Categorical data will generally be summarized with counts and percentages of patients. The denominator used for the percentage calculation will be clearly defined. Continuous data will generally be summarized with descriptive statistics including n (number of non-missing values), mean, median, standard deviation, minimum, and maximum.

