### 3.4.1 *Functional Assessments*

The CFB for functional assessments will be summarized at each scheduled time point for the following measures:

- NSAA
- NSAD
- Muscle strength test
- Timed function tests (TFTs)
  - 4-stair climb test summarized as both time and velocity (*unit=1/seconds*)
  - 100-meter timed test summarized as both time and velocity (*unit=meters/second*)
  - 10-meter walk run test summarized as both time and velocity (*unit=meters/second*)
  - Rise from supine summarized as both time and velocity (*unit=1/seconds*).

Note that the four TFT endpoints will be transformed from time to velocity (speed) as indicated by the endpoint's units. If a participant is unable to complete the TFT a velocity of "0" will be imputed.

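### Velocity change on the timed tests is averaged over the whole Safety Population, so anyone unable at baseline enters as a zero that cannot worsen and pulls the mean toward no change

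*SAP*

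**What the plan says.** **Population.** SAP 3.2.1 assigns function to the Safety Population: "The SAF will be used for all participant disposition, demographics, safety measures and functional/clinical assessments". Membership depends only on dosing: "The safety population (SAF) includes all participants who received at least one dose of EDG-5506". SAP 3.4.3 plans no subgroup summaries.

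**Inability rule.** SAP 3.4.1 covers the 4-stair climb, 100-meter, 10-meter walk/run and rise-from-supine tests: "Note that the four TFT endpoints will be transformed from time to velocity (speed) as indicated by the endpoint's units". The rule beginning "If a participant is unable to complete the TFT a velocity of" then sets the velocity to zero. It names no visit, so nothing confines it to visits after baseline. Each test is reported on two scales, for example "Rise from supine summarized as both time and velocity", but the zero is given for velocity only.

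**Change and summary.** SAP 3.1.4: "The CFB will be calculated by subtracting the BL values from the individual post-dose values". SAP 3.1.5: "Continuous data will generally be summarized with descriptive statistics including n (number of non-missing values), mean, median, standard deviation, minimum, and maximum".

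**Entry.** Protocol 5.1 has one criterion on ability, "Ambulatory at Screening (defined as ability to complete 100 meter [m] timed test, with or without assistance", and it applies only to participants who do not come from EDG-5506-001. No criterion requires anyone to climb 4 stairs, complete the 10-meter test or rise from supine.

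**The concern.** Inability at baseline is a situation the documents allow for. The zero rule presupposes inability at some visit, Protocol 8.1.1.1 adds the NSAD partly because the NSAA may have a floor, and SAP 3.5.4 provides for participants who cannot stand to be measured.

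Zero is a sensible value for someone who loses an ability during the study, because it keeps the worst outcome in the summary. At baseline it does something different. It places the participant on the floor of the scale, where no further loss can be recorded. The resulting zeros count in n and in the mean, yet they say nothing about decline.

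There is no comparator arm, Protocol 2.2.1 describes a progressive disease, and Protocol 4.3 says the functional measures will help inform dosing in later trials. A mean velocity change near zero may therefore be read as stabilisation. The planned tables do not show how many of the contributing values could not have fallen.

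**Working it through.** The plan states no figure for timed-test change or for the number unable at baseline, so there is nothing of its own to reproduce.

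**Inputs**
- n: about 8 evaluable participants is the target (Protocol 9.2, SAP 2.5). The Safety Population may be larger. As an assumed upper scenario I use n=12, the number of adults with BMD dosed by May 2022 according to Protocol 2.3.1.
- k, the number unable at baseline and throughout: not in the documents, so shown as a range.
- D, the mean change in those able at baseline: not in the documents. An assumed -0.10 1/s serves as illustration.

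**Step 1: one participant.** Unable at baseline and later: change = 0 - 0 = 0. Gains the ability at velocity v: change = v - 0 = v > 0. A negative change is impossible.

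**Step 2: the mean.** Safety Population mean = [(n-k) x D + k x 0] / n = ((n-k)/n) x D. The share of D lost is k/n.

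| k | n=8: retained / lost | n=12 (assumed): retained / lost |
|---|---|---|
| 0 | 100% / 0% | 100% / 0% |
| 1 | 87.5% / 12.5% | 91.7% / 8.3% |
| 2 | 75% / 25% | 83.3% / 16.7% |
| 3 | 62.5% / 37.5% | 75% / 25% |

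**Step 3: illustration, n=8, k=2.**
- Those able decline: 6 x (-0.10) / 8 = -0.075.
- Those able improve by the same amount: 6 x 0.10 / 8 = +0.075. The shrinkage is the same in both directions.
- Those able decline and one of the two unable participants gains 0.10: (-0.60 + 0.10 + 0) / 8 = -0.0625, so decline is masked further.
- With an assumed SD of 0.10 in those able, the SD over all eight is 0.096. The spread hardly changes and would not reveal the zeros.

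**Step 4: the median.** Take six assumed changes of -0.20, -0.15, -0.12, -0.10, -0.05 and -0.02. Their median is (-0.12 - 0.10)/2 = -0.11. With two zeros added it is (-0.10 - 0.05)/2 = -0.075. The median is not protected.

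**Step 5: could k be at least 1?** P(k >= 1) = 1 - (1-p)^n for an assumed rate p of inability on a given test.

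| p (assumed) | n=8 | n=12 |
|---|---|---|
| 5% | 34% | 46% |
| 10% | 57% | 72% |
| 20% | 83% | 93% |

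**Step 6: which tests.** Nothing in the entry criteria prevents inability on the stair climb, 10-meter or rise-from-supine test. For the 100-meter test, outside participants must have completed it at Screening, so the problem arises mainly in participants from EDG-5506-001. That study's own entry criteria are not in these documents.

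**Step 7: does the time scale solve it?** Only in part. A participant unable at baseline has no baseline time and drops out of the change in time. A participant who becomes unable later has no later time and drops out too, so the time summary omits exactly the losses that the velocity rule was written to keep.

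**The case against.** **Direction.** A reader might infer that the zeros bias the result one way, in the drug's favour. The formula does not support that. With k participants unable throughout, every mean is multiplied by (n-k)/n whatever its sign, so improvement is hidden as much as decline. Two narrower statements stand: decline is hidden if those able decline, and a participant who gains the ability pushes the mean upward.

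**Estimand.** The whole-population mean is not an error. For someone who cannot rise at either visit, a velocity change of 0 is what happened, and the mean describes all treated participants. This stands, and is why that row should be kept. It does not make the row a good measure of decline.

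**Size.** One might picture a third or half of participants unable. No document supports such a figure, and at k=0 the effect is nil. This stands. With about eight participants, however, a single one shifts the mean by 12.5%.

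**Existing safeguards.** A difference in n between the time and velocity summaries would hint at non-completers, SAP 6 promises patient-level listings of all data, and the NSAD can register decline in weaker participants. These help a careful reader. But Appendix A names no functional listing, and a difference in n does not separate inability at baseline from later loss.

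**Scope.** Only the stair climb and 100-meter test are named as endpoints in SAP 2.2; the other two are timed items within the NSAA that SAP 3.4.1 adds. The stair climb permits handrails. Both points narrow the matter without removing it, since Appendix A plans a table for each of the four tests.

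**Intent.** The zero rule may have been meant for post-baseline visits only. SAP 3.4.1 does not say so, and if that was the intent it needs stating.

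**Conclusion.** The point holds as a matter of interpretation. Applied as written, the zero rule and the whole Safety Population together give a mean velocity change equal to (n-k)/n times the mean in participants able at baseline. The loss is 12.5% to 37.5% for k=1 to 3 at n=8, 8.3% to 25% at an assumed n=12, and nothing at k=0. It concerns mainly the 4-stair climb, 10-meter and rise-from-supine velocities.

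This rests on two assumptions: that the zero rule reaches baseline, which the text permits but does not state, and that at least one participant is unable then, which the documents leave open. The outputs are exploratory and descriptive, and SAP 3.1.6 plans no hypothesis test, so no error rate, sample size or primary result is touched. A reader might also infer that the dilution alone makes results on the four tests non-comparable. The degree can differ by test, but their units already differ, so this adds little.

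**What to change.** In SAP 3.4.1:

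1. For each timed test, summarise velocity change in participants able to complete that test at baseline, keeping velocity 0 for those who later lose the ability.
2. Report at each visit the number unable at baseline, the number newly unable and the number who have gained the ability.
3. Keep the whole Safety Population row beside it.
4. State how the zero rule applies at baseline alongside the baseline carry-forward rule in SAP 3.1.4. If inability is stored as a missing result, an earlier measurement could be carried in instead of 0, and the SAP does not say which rule takes precedence.

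No new data are needed. The cost is a short addition to the SAP, a few extra rows per table, and a smaller n in the able-at-baseline rows, which is the number of participants who can inform decline. If nobody proves unable at baseline, the two rows coincide.

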### 3.2.2 *PK-Evaluable Population (PKP)*

The PK-evaluable population (PKP) includes all participants who received at least one dose of EDG-5506 and have a sufficient PK profile to derive at least one PK parameter. The PKP will be used for all summaries of PK and biomarker data.

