9.4.6. Pharmacokinetics

Treatment-experienced participants: Exposures will be summarized using descriptive statistics at each time point collected. Additional PK analysis may be done outside of the clinical study report (CSR).

Treatment-naïve participants: For Day 1, standard PK parameters endpoints will be estimated and summarized using descriptive statistics based on the PK Evaluable Population.

Exposures will be summarized using descriptive statistics at each time point collected. Additional PK analysis may be done outside of the CSR.

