### 2.2 Study Objectives and Endpoints

Primary Objective	Primary Endpoints

To assess the safety and tolerability of EDG-5506 in adults with BMD

	

Incidence, frequency and severity of adverse events (AEs), and serious adverse events (SAEs) in participants treated with EDG-5506

Secondary Objectives	Secondary Endpoints

To assess the change in individual safety parameters

	

Incidence of treatment-emergent (TE) abnormal laboratory test results (clinical chemistry, hematology, coagulation and urinalysis)

Change from baseline (CFB) in:

Safety laboratory parameters

Vital signs

Physical and neurological examinations

Cardiac function, as assessed by electrocardiogram (ECG) parameters

Cardiac function, as assessed by an echocardiogram

Pulmonary function, as assessed

	

by forced expiratory volume in one second (FEV1) and forced vital capacity (FVC)

○ Columbia Suicide Severity Rating Scale (C-SSRS)

• To assess the PK profile of EDG-5506 in adults with BMD

	

• PK concentration levels of EDG-5506

Tertiary/Exploratory Objectives	Tertiary/Exploratory Endpoints

• To investigate the effects of EDG-5506 on biomarkers of muscle fiber damage in adults with BMD

	

• CFB in biomarker measures as assessed by:

○ Serum creatine kinase (CK)

○ Serum cardiac troponin I

○ Serum myoglobin

○ Serum cardiac troponin T

○ Serum N-terminal prohormone brain natriuretic peptide (NT-proBNP)

○ Plasma troponin I tissue-specific isoforms (fast-skeletal, slow-skeletal)

○ Plasma Somascan® proteomics

• To assess the effects of EDG-5506 on functional measures in adults with BMD

	

• CFB in functional assessments, as measured by:

○ NSAA

○ NSAD

○ 4-stair climb

○ 100-meter timed test

○ Muscle strength testing

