## 3.6 Pharmacokinetics (PK)

Samples will be collected for measurement concentrations of EDG-5506 and its metabolites. Summary statistics of concentration values and associated listings will be provided.

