## APPENDIX A: TABLES, LISTINGS AND FIGURES

Table Number	Title	Population
	Subject Data and Study Conduct	
14.1.1	Participant Disposition	SAF
14.1.2	Demographics and Baseline Characteristics	SAF
14.1.3	Medical History	SAF
14.1.4	Concomitant Medications	SAF
14.1.5	Participant Exposure and Treatment Compliance	SAF
	Efficacy and Clinical Outcome Assessments	
14.2.1	NSAA	SAF
14.2.2	NSAD	SAF
14.2.3	Four-Stair Climb	SAF
14.2.4	100-meter Timed Test	SAF
14.2.5	10-m Walk/Run Test	SAF
14.2.6	Rise-From-Supine Test	SAF
14.2.7	Muscle Strength Test	SAF
14.2.8	ACTIVLIM	SAF
14.2.9	PROMIS-57	SAF
	Safety Assessments	
14.3.1	Overview of Adverse Events	SAF
14.3.2.1	Adverse Events by SOC and PT	SAF
14.3.2.2	Adverse Events by Maximum Severity, SOC and PT	SAF
14.3.2.3	Study-drug Related Adverse Events by SOC and PT	SAF
14.3.2.4	Treatment-Emergent Adverse Events Leading to Study	SAF

	Drug Discontinuation by SOC and PT	
14.3.2.5	Adverse Events Leading to Death by SOC and PT	SAF
14.3.3	Summary of Vital Signs	SAF
14.3.4.1	Summary of Clinical Laboratory Assessments: Chemistry	SAF
14.3.4.2	Summary of Clinical Laboratory Assessments: Hematology	SAF
14.3.4.3	Summary of Clinical Laboratory Assessments: Coagulation	SAF
14.3.4.4	Summary of Clinical Laboratory Assessments: Urinalysis	SAF
14.3.5	Summary of ECGs	SAF
14.3.6	Summary of DXA Assessments	SAF
	Pharmacokinetics	
14.4.1.1	Summary of Pharmacokinetics (PK) Concentrations	PK
	Biomarkers	
14.4.2.1	Summary of Biomarkers	PK

Listing Number	Title
	Disposition
16.2.1.2	Protocol Deviations
	Participant Demographics and Characteristics
16.2.4.2	Medical History
16.2.4.3	Concomitant Medications
	Exposure
16.2.5	Study Drug Exposure and Compliance
	Adverse Events

16.2.7.1.1	Adverse Events
16.2.7.1.2	Serious Adverse Events
	Other Safety Assessments
16.2.8.1	Vital Signs
16.2.8.2.1	Clinical Laboratory Assessments: Chemistry
16.2.8.2.2	Clinical Laboratory Assessments: Hematology
16.2.8.2.3	Clinical Laboratory Assessments: Coagulation
16.2.8.2.4	Clinical Laboratory Assessments: Urinalysis
16.2.8.3	ECGs
16.2.8.4	DXA
16.2.8.5	Spirometry
16.2.8.6	Physical and Neurological Examination
16.2.8.8	Echocardiogram
	Pharmacokinetics (PK) and Biomarkers
16.2.9.1.1	PK Concentrations
16.2.9.2.1	Biomarkers

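### The SAP drops the Day 1 PK parameter summary planned in Protocol 9.4.6, yet rests its PK and biomarker tables on a PK parameter it never names

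*SAP*

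**What the plan says.** **Protocol.** Section 9.4.6 treats the two groups separately. For treatment-naïve participants on Day 1, "standard PK parameters endpoints will be estimated and summarized using descriptive statistics based on the PK Evaluable Population". For the other group: "Treatment-experienced participants: Exposures will be summarized using descriptive statistics at each time point collected". The same exposure summary is planned for treatment-naïve participants. No analysis set is attached to either exposure summary. Section 9.4.5 plans change-from-baseline summaries for biomarkers and also names no set. Table 4 in section 9.3 defines the PK Evaluable Population but assigns it to no particular analysis.

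**SAP.** Section 3.2.2 admits to the PKP those who were dosed and "have a sufficient PK profile to derive at least one PK parameter". It then says: "The PKP will be used for all summaries of PK and biomarker data". The PK endpoint in section 2.2 is "PK concentration levels of EDG-5506", and section 3.6 says: "Summary statistics of concentration values and associated listings will be provided". Appendix A lists one PK table, 14.4.1.1 ("Summary of Pharmacokinetics (PK) Concentrations"), and one biomarker table, 14.4.2.1 ("Summary of Biomarkers"), both with the PK population. It lists no table or listing of PK parameters.

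**The concern.** There are two linked gaps. First, a summary that the protocol states as planned, for a secondary objective, has no counterpart in the SAP. Following the SAP as written would leave it out of the report.

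Second, the PKP is a natural set for derived parameters, but the SAP derives none. It uses the set for concentrations and biomarkers instead, so the rule for who is counted rests on a quantity that the SAP does not name.

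This matters because PK sampling differs by prior exposure, and the rule could therefore select participants by prior exposure. Protocol 9.2 justifies the sample size partly by the PK estimates it should give, and Protocol 4.2 aims to follow PK to steady state. Protocol 8.6 has biomarker samples taken from everyone, and Protocol 4.3 says biomarkers and functional measures will inform later dosing decisions. Under SAP 3.2.1 function is summarized on the Safety Population (SAF), while biomarkers carry an added PK condition for which no reason is given.

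**Working it through.** The plan gives no figure to reproduce, and no power or precision formula applies, because the study is descriptive and its size was set empirically. The check is a comparison of text plus a count of samples.

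**Step 1: planned analyses against SAP outputs.**

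| Analysis | Set named in the protocol | SAP output | Set in the SAP |
|---|---|---|---|
| Day 1 PK parameters, treatment-naïve | PK Evaluable (9.4.6) | none found in 2.2, 3.6 or Appendix A | not applicable |
| Concentrations or exposures, both groups | none (9.4.6) | Table 14.4.1.1 | PKP |
| Biomarkers | none (9.4.5) | Table 14.4.2.1 | PKP |

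The one analysis for which the protocol names the PK set is the one the SAP does not carry. The two analyses for which the SAP uses that set are ones where the protocol names none. Protocol 9.4.6 allows additional PK work outside the study report. That does not explain the gap, because the Day 1 summary is stated as planned and not as additional.

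**Step 2: is the membership rule usable within the SAP?** It requires at least one derivable PK parameter. SAP 2.2 and 3.6 cover concentrations only, and no parameter is named anywhere in the SAP. The rule therefore cannot be applied from the SAP alone, whichever protocol version is used. Protocol Table 4 has the same undefined term.

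**Step 3: who has which samples?** (Protocol Table 1 as extracted, and footnote f.)

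- Treatment-naïve, Day 1: pre-dose, 0.25, 0.5, 1, 1.5, 2, 3, 4, 6 and 24 hours = 10 samples.
- Treatment-experienced, Day 1: 1 pre-dose sample.
- Both groups later: single samples at Visits 6, 8, 10, 11, 13, 14, 15, 17 and 19 (9 visits) and Visits 21, 23, 25 and 27 (4 visits); 9 + 4 = 13.
- Urine PK: Visits 1, 6, 10 and 11 = 4, with no restriction to treatment-naïve participants. Visit 1 is screening, before dosing in this study, so 4 − 1 = 3 are on treatment.

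**Step 4: consequence.** If qualifying requires a serial profile, treatment-experienced participants fail and leave both tables, including the exposure summary that Protocol 9.4.6 plans for them. If a parameter from sparse plasma or urine samples is enough, participants with such samples qualify and the difference between the groups disappears. Neither document says which applies.

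**The case against.** The strongest reply is that the SAP is doing its job. Protocol 9.4 leaves technical detail to the SAP, SAP 1 says the SAP supersedes the protocol's statistical section, and choosing a set where the protocol is silent is legitimate. This stands in part. A reader might infer that Protocol 9.4.6 reserves the PK set for Day 1 parameters, so that both SAP tables breach it. The text does not support that: 9.4.6 contains no such exclusivity, and biomarkers fall under 9.4.5.

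A second reply is that nobody need be excluded. The aim of characterizing PK to steady state relies on the later single samples that both groups give, so a sensible analyst would accept sparse data. That is plausible, but it is a guess at a definition the SAP should state, and it does not restore the missing Day 1 summary.

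Third, Appendix A is not exhaustive. It has no C-SSRS listing although SAP 3.5.8 promises one, and under SAP 6 the table shells and programming specifications are separate documents, not available here. Absence from Appendix A alone would be weak evidence. The omission also shows in SAP 2.2 and 3.6, however, and an analysis population should be defined in the SAP itself.

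Finally, SAP 5 declares no departure from Amendment 4 (Version 5). The supplied protocol lists that amendment as history and so is later. What 9.4.6 said in Amendment 4 cannot be seen, so the declaration cannot be called false.

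**Conclusion.** The point holds and is minor. One protocol-planned summary is missing from the SAP, and the two tables for PK and biomarkers use a set whose qualifying parameter is undefined. For biomarkers and concentrations this is an unexplained restriction, not a conflict with the protocol.

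A reader might go further and infer that most of the sample is lost. Protocol 4.2 counts 5 adults with BMD dosed before this study, and 8 − 5 = 3 would leave 5/8 = 62.5% excluded. The documents do not support that figure. It assumes that all 5 enrolled, that the total is exactly 8 and that all 5 fail an undefined test. The 12 adults with BMD in Protocol 2.3.1 are all those ever dosed, not the enrolment here. The loss could be zero, and the number affected cannot be determined.

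The effect is confined to descriptive tables for secondary (PK) and exploratory (biomarker) endpoints. No hypothesis is tested, and Listings 16.2.9.1.1 and 16.2.9.2.1 keep the individual data.

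**What to change.** - Add the Day 1 PK parameter summary, for participants with serial sampling, to SAP 3.6 and Appendix A on the PKP, and name the parameters. AUC0-24 is in the protocol's abbreviation list and is one candidate, although the protocol does not name it as an endpoint.
- Summarize biomarkers on the SAF using observed data.
- Summarize concentrations on all treated participants with at least one measured concentration.
- Change the population column for Tables 14.4.1.1 and 14.4.2.1 to match.
- Check SAP 5 against the current protocol version and list any difference that remains.

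The choice of set for biomarkers and concentrations is a recommendation, since the protocol requires none. If the sponsor prefers to keep the PKP there, SAP 3.2.2 should say which parameter qualifies a participant, whether sparse or urine samples count, and why biomarkers need a PK condition.

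The cost is minor rewording in SAP 3.2.2 and 3.6 (and 5 if needed), two changed table entries and one extra table. The samples are already scheduled, so no new data are needed.
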